#### **Cohort 4 expansion group:**

An SRC meeting was convened after the 10 subjects in Cohort 4 completed the Safety Assessment and approved the following:

- Up to 20 additional subjects (for a total of approximately 30 subjects) will be enrolled into Cohort 4.
- After each treatment, the additional subjects enrolled into Cohort 4 expansion: will remain in the study center for up to 1-hour (reduced from 2-hours) post second injection for safety monitoring (e.g., continuous blood pressure, electrocardiographic and AE monitoring), an additional hour may be continued at the discretion of the PI.

#### **Cohort 5 expansion group:**

An SRC meeting was convened after the 10 subjects in Cohort 5 completed the Safety Assessment and approved the following:

- Up to 20 additional subjects (for a total of approximately 30 subjects) will be enrolled into Cohort 5.
- After each treatment, the additional subjects enrolled into Cohort 5 expansion: will remain in the study center for up to 1-hour (reduced from 2-hours) post second injection for safety monitoring (e.g., continuous blood pressure, electrocardiographic and AE monitoring), an additional hour may be continued at the discretion of the PI.

Plasma PK sampling will be collected in subjects in Part 2 (Cohorts 4 and 5 expansion group) as detailed in Table 8-1.

Four to 6 weeks in Part 1, and 12 to 14 weeks (Part 2) after the first injection of VP-315, subjects will return for all target and nontarget BCC lesions (Section 5.4) to be excised for histological evaluation. If the lesion(s) has clinically cleared, the area where the lesion was will be excised, and tissue samples will be sent to the central dermatopathologist for analysis/histology. Suture removal and final photography should occur 7 (±1) or 14 (±2) days after excision (7 days on the face and 14 days on the body). Subjects with excised lesions on both the face and the body will be required to complete 2 end-of-study (EOS) visits accordingly.

During the study period, subjects will be expected to visit the study facility and complete study procedures as outlined in the schedule of assessments (Table 8-1).

If there is a clinically significant AE or abnormal laboratory result at the EOS visit, follow-up (F/U) visits may be required until resolution of the abnormality, or until the condition is considered clinically stable.

#### 4.2 Number of Sites

There will be up to 15 study sites in the US that will participate in this study.

## 4.3 Estimated Study Duration

#### 4.3.1 Study Duration for Subjects

The treatment duration for each subject is variable—each subject will receive VP-315 for up to a maximum of 2 weeks. In Part 1, in the event of DLT or necrosis of all target lesions, treatment will be stopped.

All lesions will be excised 4 to 6 weeks (Part 1) and 12 to 14 weeks (Part 2) after the W1D1 injection. The study duration for each subject is variable as a subject may require F/U visit at 1- or 2- weeks post-excision.

The study will require approximately 17 months from the time that the first subject provides signed informed consent through the last subject's last study-related visit (up to 42 days Screening; treatment in 1-week intervals until visual confirmation of necrosis of target lesions; surgical excision of all target and nontarget lesions 4 to 6 weeks (Part 1) and 12 to 14 weeks (Part 2) after W1D1 injection; F/U visit at 1 or 2 weeks post-excision).

## 4.3.2 End of Study

Surgical excision of all target and nontarget BCC lesions will occur 4 to 6 weeks (Part 1) and 12 to 14 weeks (Part 2) after the W1D1 injection, and a F/U visit will take place 1- or 2- weeks post-excision (EOS visit). Suture removal and final photography should occur 7 (±1) or 14 (±2) days after excision (7 days on the face and 14 days on the body). Subjects with excised lesions on both the face and the body will be required to complete 2 EOS visits accordingly. Scar Cosmesis Assessment and Rating (SCAR) Scale will be completed by the site investigator prior to excision at the EOS Visit (Part 2: Cohorts 4 and 5).

### 5. STUDY POPULATION

Before any study-specific procedure may be performed, the appropriate written informed consent must be obtained (see Section 12.2).

Investigators will be expected to maintain a screening log in the electronic CRF of all potential study candidates who sign the informed consent form (ICF) that includes limited information about the potential candidate (age, gender, race), date, and outcome of the screening process (e.g., enrolled into study, reason for ineligibility, or refused to participate).

# 5.1 Number of Subjects

### Safety Run-in (Part 1 of the Study)

Approximately 2-8 subjects with a histological diagnosis of BCC will be enrolled for treatment with VP-315 in Part 1.

#### **Dosing Regimen Optimization and Confirmation (Part 2 of the Study)**

Approximately 66-72 subjects with a histological diagnosis of BCC will be enrolled for treatment with VP-315 in Part 2.

# 5.2 Subject Inclusion Criteria

Subjects must meet all of the following inclusion criteria to be eligible for participation in this study:

- 7. Adults ≥18 years of age
- 8. Clinically suspected BCC with at least 1 (and up to 5) eligible lesion(s) suitable for biopsy and excision (see Section 5.4)
- 9. Willing to refrain from using nonapproved topical agents on, or within 2 cm of, the target BCC lesions and surrounding areas during the treatment period. Subjects should use topical agents that are gentle (e.g., Aquaphor®, CeraVe®) and will not irritate the skin in these areas
- 10. Willing to refrain from exposure to direct sunlight or ultraviolet light and to avoid the use of tanning parlors for the duration of the study
- 11. Written informed consent obtained, including consent for tissue to be examined by the central dermatopathologist and stored by the Sponsor or designee
- 12. Willing to undergo BCC surgical excision procedure of target and nontarget BCC lesions after study treatment
- 13. Willing to delay surgical excision of target and nontarget BCC lesions until the end of treatment (EOT) visit

- 14. Provides written consent to allow photographs of the target and nontarget BCC lesion to be used as part of the study data
- 15. Willing to practice a highly effective method of birth control while on study and until 4 weeks after the last treatment. Highly effective birth control includes sexual abstinence, vasectomy, bilateral tubal ligation/occlusion, or a condom with spermicide (men) combined with hormonal birth control or intrauterine device in women.

# 5.3 Subject Exclusion Criteria

Subjects who meet any of the following exclusion criteria are not to be enrolled in this study.

- 1. Presence of known or suspected systemic cancer
- 2. Treatment with systemic chemotherapeutic agents within the 6 months prior to the screening visit
- 3. Treatment with systemic immunotherapy, immunomodulators or immunosuppressants within the 12 weeks prior to the screening period
- 4. Genetic or nevoid conditions (e.g., Gorlin / basal cell nevus syndrome, xeroderma pigmentosum
- 5. Clinically significant laboratory values, as assessed by the investigator, for the tests listed in the Schedule of Assessments, including:
  - a. serum creatinine  $>1.5\times$  the upper limits of normal and
  - b. serum tryptase concentration >11.4 ng/mL
- 6. Chronic medical condition such as, but not limited to:
  - a. Uncontrolled infection or infection requiring antibiotics
  - b. Uncontrolled cardiac failure: Classification III or IV New York Heart Association
  - c. Subjects presenting with a systolic BP <110 mmHg and/or diastolic BP <70 mmHg at Screening or Week 1 Day 1 or a history of cerebrovascular or cardiac disorders, or subjects at particular risk of sequelae following a short hypotensive episode.
  - d. Uncontrolled systemic or gastrointestinal inflammatory conditions
  - e. Known bone marrow dysplasia
  - f. History of positive tests for human immunodeficiency virus/acquired immunodeficiency syndrome or active hepatitis B or C
  - g. History of systemic autoimmune disease requiring anti-inflammatory or immunosuppressive therapy within 3 months prior to Day 1, with the following exceptions:
    - i. Subjects with a history of autoimmune thyroiditis are eligible provided the subject requires only thyroid hormone replacement therapy and disease has been stable for ≥1 year

- ii. Subjects with well-controlled type I diabetes (in the opinion of the investigator) are eligible
- h. Known mast cell activation syndrome, mastocytosis, or chronic idiopathic urticaria
- 7. Known sensitivity to any of the ingredients in the study medication
- 8. Elective surgery within 4 weeks prior to the screening visit, during the study, or 4 weeks after the treatment period
- 9. Evidence of current chronic alcohol or drug abuse
- 10. Current enrollment in an investigational drug or device study or participation in such a study within 4 weeks of the screening visit
- 11. In the investigator's opinion, evidence of unwillingness, or inability to follow the restrictions of the protocol and complete the study
- 12. Females who are pregnant or breastfeeding.

## 5.4 BCC Lesion Eligibility

Eligible lesions are those that meet the BCC lesion eligibility specifications described herein, from samples that are either from:

- *HISTORICAL* punch or shave biopsies (i.e., samples collected according to clinical standard of care collected within the 90 days prior to W1D1);
- A 2-mm punch biopsy collected within 90 days of W1D1 for suspected BCC ≥0.5 cm to 1.0 cm, and 3-mm punch biopsy for suspected BCC >1.0 cm to 2.0 cm; or
- A shave biopsy performed according to standard of care to include superficial or middle papillary dermis collected within 90 days of W1D1.

Lesions must meet the following criteria to be eligible for treatment with VP-315 as target lesions or for observation as nontarget lesions. Up to 2 target lesions may be treated, and any eligible lesions that do not receive treatment (up to 3) will be tracked as nontarget lesions for abscopal effect.

Lesions that meet the inclusion criteria and are only excluded by Criteria 6 through 9 in Section 5.4.2 below (TARGET LESION EXCLUSION) may be tracked as nontarget lesions. Lesions that do not meet the inclusion criteria or are excluded by BCC Lesion Exclusion Criteria 1 through 5 below will not be treated or observed (i.e., ineligible) and should be excised after completion of the study unless otherwise clinically indicated.

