#### 5.4.2 BCC Lesion Exclusion Criteria

- 1. Recurrent or previously treated lesions
- 2. Lesions within 1 cm of the eyelids or lips, or on the hands, feet, ears, nose, and genitalia
- 3. Histological evidence of any other tumor in the biopsy specimen
- 4. Histological evidence of infiltrative, desmoplastic, sclerosing, or morpheaform BCC subtypes in the biopsy specimen
- 5. Medium- and high-risk basal cell carcinomas as defined by the National Comprehensive Cancer Network (NCCN) or Mohs Appropriate Use Criteria (i.e., BCCs eligible for Mohs surgery).

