### TARGET LESION EXCLUSION ONLY:

- 6. For subjects with severe stasis dermatitis, target BCC lesions may not be on the lower extremities
- 7. Within 2 cm of the target BCC lesion(s):
  - a. Treatment with the following topical agents within the 12 weeks prior to the screening visit: aminolevulinic acid, 5-fluorouracil, corticosteroids, diclofenac, imiquimod, ingenol mebutate
  - b. Treatment with surgical excision, or curettage within the 2 weeks prior to the screening visit
  - c. Evidence of dermatological disease or confounding skin condition that may interfere with clinical evaluation (i.e., psoriasis, atopic dermatitis, eczema, propensity to form keloids or hypertrophic scarring)
  - d. Use of topical immunomodulators during study
- 8. Within 5 cm of the target BCC lesion(s): history of any skin cancer, except for other currently identified target and nontarget BCC lesions
- 9. Target BCC lesion is in the area of prior resurfacing procedure with CO2 laser or any photodynamic and phototherapy treatment within the 3 months prior to the screening visit.

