#### 7.6 Treatment Restrictions

#### 7.6.1 Prohibited Medications

All prescription medications (other than those specifically excluded in Section 5.3 (Exclusion Criteria) that subjects have been prescribed will be continued during the subject's participation in the study.

Subjects should be advised to avoid the use of excluded medications and treatments. If, in the opinion of the investigator, a subject requires any of these medications, the Medical Monitor should be consulted.

Nonapproved topical agents should not be used on, or within 2 cm of, the target BCC lesions and surrounding areas during the treatment period and through the EOS visit.

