### **8.4. Abscopal Effect Based on Non-treated Lesions at Excision**

An abscopal effect is a phenomenon whereby the treatment of target lesions leads to improvement in both treated and non-treated lesions.

A summary of (a) histologic clearance and (b) clinical clearance for non-treated lesions will be provided to investigate a possible abscopal effect using EOT data and the full analysis population.

The histologic clearance will follow Section 8.1 of this SAP except for using the histologic diagnosis of excised non-treated lesions (NTL1, NTL2, NTL3), and the clinical clearance will follow Section 8.2 of this SAP except for using the PGA of non-treated lesions (NTL1, NTL2, NTL3). The summary will be provided by clearance (Histologic, Clinical) within lesion (NTL1, NTL2, NTL3). The summary will also be run using the per-protocol population as outlined in Section 6 of this SAP.

A separate listing will be provided for the excision of all lesions as described in Section 8.1 of this SAP, and a separate listing will be provided for the PGA of all lesions as described in Section 8.2 of this SAP.

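### Local therapy used during the study on or near a nontarget lesion is neither restricted by lesion nor handled in SAP 8.4, so clearance it causes would be counted as abscopal

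*Protocol*

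**What the plan says.** Protocol Section 5.4.2 has two blocks of lesion exclusions. Criteria 1 to 5 bind every lesion: Section 5.4 says that lesions "excluded by BCC Lesion Exclusion Criteria 1 through 5 below will not be treated or observed", and criterion 1 reads "Recurrent or previously treated lesions". Criteria 6 to 9 bind target lesions only, because otherwise eligible lesions that "are only excluded by Criteria 6 through 9 in Section 5.4.2 below (TARGET LESION EXCLUSION) may be tracked as nontarget lesions".

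Three items in the target-only block concern local therapy:

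- **7a**, within 2 cm of the lesion: "Treatment with the following topical agents within the 12 weeks prior to the screening visit: aminolevulinic acid, 5-fluorouracil, corticosteroids, diclofenac, imiquimod, ingenol mebutate".
- **7d**, within 2 cm of the lesion: "Use of topical immunomodulators during study".
- **9**, a lesion in an area of CO2 laser resurfacing or "any photodynamic and phototherapy treatment within the 3 months prior to the screening visit".

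During the study, Section 7.6.1 says "Nonapproved topical agents should not be used on, or within 2 cm of, the target BCC lesions and surrounding areas during the treatment period", and extends this to the end-of-study visit. The inclusion criterion on topical agents in Section 5.2 has the same scope. Neither names nontarget lesions.

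On analysis, SAP 8.4 states: "A summary of (a) histologic clearance and (b) clinical clearance for non-treated lesions will be provided to investigate a possible abscopal effect". It uses end-of-treatment data for NTL1, NTL2 and NTL3 in the full analysis population, repeated in the per-protocol population. It has no rule for an NTL that received another local therapy.

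**The concern.** Abscopal effect is a secondary efficacy endpoint in Part 2 and exploratory in Part 1. Its evidence is the clearance of lesions that were not injected, in an open-label study with no reference product. No concurrent group would show how often such lesions clear for other reasons.

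The protocol regards local therapy near a lesion as enough of a disturbance to disqualify a target lesion. It then waives that protection for the lesions that carry the abscopal endpoint. If a therapy with activity against BCC is used on or beside an NTL in the 12 to 14 weeks before excision, the resulting clearance would be credited to VP-315. An agent that helps clear BCC can only raise the apparent NTL clearance rate, so the error would favour an abscopal signal.

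**Working it through.** The documents state no figure on this point. The check is to apply each rule to an NTL.

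| Exposure of an NTL | Governing rule | Result |
|---|---|---|
| Lesion itself treated before the study | 5.4.2 criterion 1, no time limit; synopsis says the same for target and nontarget lesions | Ineligible |
| Listed topical agent within 2 cm in the 12 weeks before screening, lesion itself untreated | 7a, target only | May be tracked |
| Lesion in a recent photodynamic, phototherapy or laser field, lesion itself untreated | Criterion 9, target only | May be tracked |
| Topical immunomodulator within 2 cm during the study | 7d, target only | May be tracked |
| Other topical therapy on or near the NTL during the study | 5.2 and 7.6.1 name target lesions; 7.5 speaks of supportive care | No lesion-level restriction |
| Ultraviolet exposure during the study | 7.6.2, whole subject | To be avoided |
| Excision before end of treatment | 5.2, target and nontarget | Not allowed |

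An NTL within 2 cm of a target lesion is protected incidentally; others are not. Section 7.6.2 names ultraviolet light but not photodynamic therapy. Section 7.6.1 also tells subjects to avoid excluded medications, but refers to Section 5.3, whose drug exclusions read as systemic agents.

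**Can an exposed lesion be identified?** Protocol 7.5 records drug name, indication, quantity and dates. SAP 7.4 lists prior and concomitant therapies with indication, dose, route and dates. SAP 7.5 lists earlier BCC treatment by type, with a category for topical treatment, and the date of the latest. SAP 7.3 lists lesion locations. An exposed subject can therefore be found. No listing gives the application site, so the exposure cannot be tied to a particular lesion.

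**Would another analysis separate them?** The closest example in SAP Section 6 of a major deviation is use of a prohibited medication, and use near an NTL is not clearly prohibited. SAP 5.4 and 5.5 plan no covariate analyses and no further subgroups. The sensitivity analysis in SAP 8.7 deals only with missing values.

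**Size.** If one NTL in a row of n is cleared by the other therapy and would not otherwise have cleared, the row rises by 1/n. The number of NTLs is not given. Assumed values:

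- n = 10: 1/10 = 10 points
- n = 20: 1/20 = 5 points
- n = 40: 1/40 = 2.5 points

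A floor follows from SAP Section 3, since each subject has at most one NTL1 and so n cannot exceed the cohort size:

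- Cohort 4 or 5 initial group (10 subjects): at least 1/10 = 10 points
- Cohort 4 expansion (26): at least 1/26 = 3.8 points
- Cohort 5 expansion (27): at least 1/27 = 3.7 points
- Part 2 total (82): at least 1/82 = 1.2 points

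SAP Section 8 notes that not every subject has further lesions, so real rows will usually be smaller and the shift larger.

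**The case against.** The strongest reply is that the gap is narrow and the exposure unlikely. Criterion 1 bars any NTL itself treated before the study and is stricter than the windows in 7a and 9. Those two criteria look back from screening; only 7d is an on-study rule. Protocol 7.5 frames concomitant treatment as supportive care, and subjects have agreed to have their NTLs excised at end of treatment, so there is little reason to treat one separately. Each NTL needs a histological diagnosis of BCC within 90 days of W1D1, and nothing in the documents shows that therapy of neighbouring skin clears a lesion. The endpoint is descriptive and no decision rule depends on it.

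Most of this stands. It makes pre-study exposure the lesser route, though it does not remove it: a biopsy 90 days before W1D1 precedes a day -42 screening visit by 90 - 42 = 48 days, so neighbouring therapy can come after the biopsy. It does not close the on-study route, where 7d is expressly waived and no topical rule names NTLs.

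A reader might infer more than the documents support:

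- **That NTLs are free of every ban on 5-FU, imiquimod, aminolevulinic acid or photodynamic therapy.** Criterion 1 rules this out for direct pre-study treatment.
- **That exposed cases cannot be traced.** The listings show drug, indication, route and dates; only the site is missing.
- **That the per-protocol set could never remove them.** The SAP's list of deviations is not exhaustive and includes subject compliance, so removal is possible. Nothing prompts it.
- **That every 7a exposure should disqualify an NTL.** 7a also covers corticosteroids and diclofenac, and the documents do not show that these favour clearance.

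**Conclusion.** The point holds in limited form. A written exemption, together with an on-study topical restriction confined to target lesions, lets an NTL exposed to another local therapy enter the abscopal summary unmarked. The main route is on-study therapy on or near an NTL; the second is pre-study therapy of skin within 2 cm or of a photodynamic or laser field.

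The likely number of exposed lesions cannot be estimated, and nothing shows that any exposure occurred. The effect of one falsely cleared lesion is 1/n, large in the small rows that SAP 8.4 will produce.

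The direction of bias rests on the assumption that the therapy concerned can clear BCC. The protocol's exclusion of these therapies around target lesions and the SAP's category of topical treatment for earlier BCC make that reasonable, but the documents do not quantify it. The matter should be settled before lock. It affects only the abscopal endpoint and does not touch the results for treated lesions.

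**What to change.** Before database lock, add to SAP 8.4:

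1. An NTL is flagged as exposed if topical or light-based therapy with potential anti-BCC activity (for example imiquimod, 5-FU, aminolevulinic acid or photodynamic therapy) was used on it or within 2 cm during the study, or if it had pre-study exposure of that kind under 7a or 9. Corticosteroid or diclofenac use alone does not set the flag.
2. Candidate subjects are found from the medication and prior-treatment listings, and the application site is obtained by site query. The flag is set without reference to the NTL's clearance result.
3. Flagged NTLs are listed with agent, dates, site and excision result.
4. The abscopal summary is shown with and without flagged NTLs, and any abscopal conclusion rests on the unexposed ones.

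If the protocol is amended again, Section 5.4 should state that such lesions are not evaluable for the abscopal endpoint. Their observation and excision need not change.

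The cost is a site query, a flag, a listing and a repeat display. A few NTLs leave the denominator of the second display. Removing lesions for on-study exposure is selection after baseline and can bias in its own way, which is why both summaries are needed. If the query finds no exposed NTL, one sentence saying so closes the point.

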# 5.4.1 BCC Lesion Inclusion Criterion

1. For punch biopsies: the size of the lesion(s) must be  $\geq 0.5$  cm and  $\leq 2$  cm in the longest diameter prior to punch biopsy.

2. Histological diagnosis of nodular, micronodular, or superficial BCC, as confirmed by punch or shave biopsy performed within 90 days of W1D1. (NOTE: *HISTORICAL* punch or shave biopsies are acceptable, provided that the biopsy was performed according to clinical standard of care and was collected within the 90 days prior to Screening W1D1.)

